7.1. Adverse Events

7.1.1. Definition of Adverse Events

An AE is defined as any untoward medical occurrence associated with the use of a drug in humans, whether or not considered to be drug related. An AE can therefore be any unfavorable and unintended sign, symptom, or disease temporally associated with the use of an investigational product, whether or not thought to be related to the investigational product. An AE may also constitute complications occurring as a result of protocol-mandated interventions (eg, invasive procedures such as biopsies), including the period prior to receiving the first dose of the study drug (eg, medication washout). In addition to new events, any increase in the severity or frequency of a preexisting condition that occurs after the participant signs the ICF is considered to be an AE. This includes any side effect, injury, toxicity, or sensitivity reaction.

A suspected adverse reaction is any AE for which there is a reasonable possibility that the drug caused the AE. For the purposes of expedited safety reporting, "reasonable possibility" means there is evidence to suggest a causal relationship between the drug and the AE. Suspected adverse reaction implies a lesser degree of certainty about causality than adverse reaction, which means any AE caused by a drug.

Life-threatening AE or life-threatening suspected adverse reaction is an AE or suspected adverse reaction that, in the view of either the investigator or sponsor, places the study participant at immediate risk of death. It does not include an AE or suspected adverse reaction that, had it occurred in a more severe form, might have caused death.

An AE or suspected adverse reaction is considered to be "unexpected" if it is not listed in the Reference Safety Information (RSI) section of the current IB or is not listed at the specificity or severity that has been observed.

An SAE or serious suspected adverse reaction is an AE or suspected adverse reaction that, at any dose, in the view of the either the investigator or sponsor, results in any of the following outcomes:

- Death
- A life-threatening AE
- Inpatient hospitalization or prolongation of existing hospitalization
- Persistent or significant incapacity or disability (substantial disruption of the ability to conduct normal life functions)
- A congenital anomaly/birth defect
- Important medical events that may not result in death, be immediately life-threatening, or require hospitalization may be considered serious when, based upon medical judgment, they may jeopardize the study participant and may require

medical or surgical intervention to prevent one of the outcomes listed in this definition.

NOTE: Hospitalization planned prior to study enrollment (eg, for elective surgeries) is not considered to be an SAE. Hospitalizations that occur for pre-existing conditions that are scheduled after study enrollment are considered SAEs.

The investigator will assess each AE for seriousness, severity, and relationship to investigational product.

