6.13. Transcranial Doppler Ultrasonography

Transcranial Doppler assessments performed as part of standard of care will be recorded on the eCRF. Participants having an abnormal TCD (ie, ≥ 200 cm/sec) during the study will be treated according to the institution's standard of care (eg, initiation of HU or chronic transfusions). Continuation of voxelotor is at the discretion of the investigator.

For participants who discontinued Study GBT440-032 (HOPE Kids 2) as a result of an abnormal TCD \geq 200 cm/sec, TCD assessments will be performed using a Multi-Dop T digital machine manufactured by Compumedics DWL (Germany).

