4. STUDY ENDPOINTS

Safety:

• Treatment-emergent adverse events (TEAEs) and serious adverse events (SAEs)

Sickle Cell Disease-Related Complications:

• Frequency of SCD-related complications

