8.2.2 Adverse Events

All AEs will be coded using MedDRA (current version). Adverse events reported for participants participating in this study will be graded using the National Cancer Institute's (NCI) Common Terminology Criteria for Adverse Events (CTCAE), version 5.0. For AEs not adequately addressed in the NCI CTCAE, version 5.0, protocol-specified criteria will be used.

All adverse events summaries described below will be presented for both non-SCD and SCD-related TEAEs.

Non-SCD-related TEAE summary tables will exclude SCD related events including but not limited to the preferred terms of: sickle cell anemia with crisis, acute chest syndrome (ACS), pneumonia, priapism, splenic sequestration, hepatic sequestration, stroke, leg ulcers, dactylitis, and osteonecrosis. Additional TEAE tables will summarize the aforementioned SCD related events.

Overall summaries will be presented which include the number of TEAEs and the number and percentage of participants who experienced at least one TEAE. The summaries will also include TEAEs Grade 3 or greater, TEAE related to study drug, TEAEs leading to study drug reduction, TEAEs leading to study drug interruption, TEAEs leading to discontinuation of study drug, and SAEs. TEAEs leading to deaths will be summarized together regardless if they are SCD-related, as cause of death may include multiple TEAEs.

Additional summaries of TEAEs will be provided showing the number and percentage of participants who experienced at least one TEAE. These summaries will be presented by MedDRA System Organ Class (SOC), Preferred Term (PT) and maximum severity. If a participant reports the same PT multiple times within the same SOC, that PT will only be counted once within that SOC for that participant. As with the PT, if a participant reports multiple conditions within the same SOC, that SOC will only be counted once for that participant.

The occurrence of TEAEs assessed as related to voxelotor by the investigator will be tabulated by SOC, PT, and maximum severity. Serious adverse events will be presented by SOC, PT, and maximum severity.

Grouped terms for rash and abdominal pain will be summarized.

Adverse events recorded in the CRF which began prior to first dose of study drug will not be included in the summary tables.

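### The SAE note in Protocol 7.1.1 makes an SAE of any admission for a pre-existing condition scheduled after enrolment, worsened or not; this contradicts the section's own AE definition, and SAP 8.2.2 removes only some of the resulting records

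*Protocol*

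**What the plan says.** Protocol 7.1.1 builds its definitions in steps. An AE has to be untoward: "An AE is defined as any untoward medical occurrence associated with the use of a drug in humans". For a condition already present, the trigger is a change: "any increase in the severity or frequency of a preexisting condition that occurs after the participant signs the ICF is considered to be an AE". An SAE is then an AE (or suspected adverse reaction) that leads to one of the listed outcomes, among them inpatient hospitalization.

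The note after that list covers planned admissions in two sentences. The first is an exemption: "Hospitalization planned prior to study enrollment (eg, for elective surgeries) is not considered to be an SAE". The second is the opposite case: "Hospitalizations that occur for pre-existing conditions that are scheduled after study enrollment are considered SAEs". Neither mentions worsening.

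SAEs are a named safety endpoint beside TEAEs (Protocol 8.1.1; SAP 4). In SAP 8.2.2, "Serious adverse events will be presented by SOC, PT, and maximum severity". The same section introduces its AE summaries as summaries of TEAEs, shown separately for SCD-related and other events, and leaves out AEs with onset before first dose. SAP 5 counts an event as treatment-emergent if it is new since study drug began or is an earlier event that has become worse on treatment. Protocol 7.3 requires every SAE to be reported within 24 hours, whatever its cause.

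**The concern.** Every participant enters with SCD, so every participant has a pre-existing condition, and Protocol 3.2 sets no fixed length of treatment. Elective admissions for existing disease can therefore be booked after enrolment. Under the note, the same operation for the same unchanged disease is not an SAE if it was planned before enrolment and is one if it was scheduled after. The booking date decides, and that date carries no information about safety.

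The study has one arm and is purely descriptive (Protocol 8), so the absolute SAE incidence is itself the result and no control group would show the same addition. SAP 6.3 allows interim safety summaries to support regulatory applications. Planned care counted as SAEs would overstate harm in those figures.

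**Working it through.** The plan states no SAE rate, event count or power figure, so there is nothing to reproduce. The check compares the rules, follows a record through to the tables, and then sizes the effect.

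**Step 1. The two rules in Protocol 7.1.1, side by side.**

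| Admission for a pre-existing condition | AE under the definition? | SAE under the note? |
|---|---|---|
| Planned before enrolment, condition unchanged | No | No |
| Scheduled after enrolment, condition unchanged | No | Yes |
| Scheduled after enrolment, condition worsened after consent | Yes | Yes |

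The second row is the contradiction: an SAE that is not an AE. The note's two sentences differ only in when the admission was planned, so timing is the only test it states.

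**Step 2. What reaches the SAE tables.** Take a second-row admission that the site reports as the note instructs.

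- Recorded under the old condition with its original onset: it began before first dose and has not worsened, so it is removed by the SAP 8.2.2 onset rule and is not a TEAE under SAP 5.
- Recorded as an event of its own (the admission or the procedure) with an on-study onset date: it was absent before treatment and started after first dose, so it passes both filters and is tabulated.

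Neither document says which way to record it. In both cases the 24-hour report in Protocol 7.3 is triggered.

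**Step 3. Effect per participant.** Input: up to about 600 participants (Protocol 3.1), all assumed dosed and so in the safety population. One participant whose only SAE is such an admission adds

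1/600 = 0.00167 = 0.17 percentage points.

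Because SCD-related and other events are shown separately, the only SAE means the only one in that set of tables. Ten such participants add at most 10/600 = 1.7 points, however often each is admitted, because SAP 8.2.2 counts a participant once per SOC and PT. Repeats can show only in the event counts of the overall summary.

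**Step 4. Range under assumed rates.** The documents give neither the rate r of planned admissions per participant-year nor the follow-up T in years, so both are assumptions. All such admissions are taken to pass the filters in Step 2.

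- Extra SAE records = 600 × r × T
- Share with at least one: p = 1 − exp(−rT)
- Rise in incidence = (1 − s) × p, where s is the share with another SAE anyway (assumed independent, 30% or 50%)

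| r | T | Extra records | p | Rise, s = 30% | Rise, s = 50% |
|---|---|---|---|---|---|
| 0.01 | 1 | 600 × 0.01 × 1 = 6 | 1.0% | 0.7 points | 0.5 points |
| 0.05 | 2 | 600 × 0.05 × 2 = 60 | 9.5% | 6.7 points | 4.8 points |
| 0.10 | 4 | 600 × 0.10 × 4 = 240 | 33.0% | 23.1 points | 16.5 points |

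The spread shows that the size turns entirely on a rate the documents do not supply.

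**The case against.** **The SAP already applies a worsening test.** SAP 8.2.2 says that all the AE summaries it goes on to describe are for TEAEs, the SAE table is among them, and a pre-treatment event must have become worse to be a TEAE. This stands for records dated to the old condition. It does not stand for an admission entered as a new event with an on-study date, and it does not touch the reporting duty. SAP 2 lets the SAP override the protocol's statistical methods; what sites must report is not one of those.

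**The note can be read in sequence.** It sits inside a definition that begins with AE status, so it might only say which hospitalizations of an existing AE are exempt. That reading is possible, but the second sentence carries no such condition and says outright that these admissions are SAEs. Sites that differ on the reading would report differently.

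**A date rule is conservative and reproducible.** In an uncontrolled long-term safety study that is a fair reason to report widely. It is not a reason to count non-AEs in the endpoint.

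**Transfusion programmes.** A reader might infer that a participant admitted for transfusion every 4 weeks yields 52/4 = 13 SAE records a year. The documents do not support this. Protocol 6.13 mentions transfusion only as an example of care after an abnormal TCD during the study ("eg, initiation of HU or chronic transfusions"), which may itself be a new or worsened finding. No inpatient setting or 4-weekly schedule is stated. Protocol 3.3.2.2 names the start of chronic transfusion as a situation in which the investigator may stop voxelotor, and AE recording ends 28 days after the last dose. RBC transfusions also have their own CRF (SAP 5).

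**Conclusion.** The note in Protocol 7.1.1 is wrong as written: it makes SAEs of events that the same section does not make AEs. The severity is minor. The SAP's filters remove part of the effect; what remains is planned admissions recorded with an on-study onset, plus 24-hour reports with no untoward event behind them. The firm figure is 0.17 percentage points per affected participant with no other SAE, assuming 600 in the safety population; with fewer participants it is 1/N. The range in the working rests on assumed rates and is an illustration.

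A reader might go further and infer that planned care dominates the SAE endpoint, or that SAE results cannot be compared between countries or originating studies. The documents support neither. They give no frequency of planned admissions, admissions planned before enrolment are already exempt, the SAP plans no SAE comparison by country, and summaries by antecedent study are only optional (Protocol 8). With no formal tests planned, error rates and power are not affected.

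**What to change.** Either of two changes would do.

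1. Reconcile the note with the AE definition in Protocol 7.1.1, so that a planned admission for a pre-existing condition counts in the SAE endpoint only if the condition worsened or a new untoward event occurred.
2. Leave SAE reporting unchanged, add a flag to the AE/SAE eCRF for a planned admission without worsening, and have SAP 8.2.2 present SAEs with and without the flagged records.

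The first costs one protocol sentence; the second costs one eCRF field and one repeated SAE table. With either, the investigator must judge whether the condition worsened, and some true worsening could be missed. The second option limits that risk because every record is still reported and shown. Both concern event classification only.

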7.1.2. Severity of Adverse Events

Whenever possible, the severity of all AEs will be graded using the National Cancer Institute Common Terminology Criteria for Adverse Events (NCI CTCAE), Version 5.0.

For AEs not adequately addressed in the NCI CTCAE, Version 5.0, the criteria presented in Table 11 should be used.

Table 11: Grading for Adverse Events Not Covered in the NCI CTCAE

Severity	Description
Grade 1 – Mild	Asymptomatic or mild symptoms; clinical or diagnostic observations only; intervention not indicated
Grade 2 – Moderate	Minimal, local or noninvasive intervention indicated; limited age-appropriate instrumental ADLs
Grade 3 – Severe	Medically significant but not immediately life threatening; hospitalization or prolongation of hospitalization indicated; disabling; limiting self-care ADLs
Grade 4 – Life Threatening	Life-threatening consequences; urgent intervention indicated
Grade 5 – Fatal	Death

Abbreviations: ADL, activity of daily living; NCI CTCAE, National Cancer Institute Common Terminology Criteria for Adverse Events.

To make sure that there is no confusion or misunderstanding between the terms "serious" and "severe", which are not synonymous, the following note of clarification is provided. The term "severe" is often used to describe the intensity (severity) of a specific event (ie, mild, moderate, or severe); the event itself, however, may be of relatively minor medical significance (eg, severe headache). This is not the same as "serious", which is based on the study participant/event outcome or action criteria associated with events that pose a threat to a participant's life or functioning. Seriousness (not severity) serves as a guide for defining regulatory reporting obligations.

7.1.3. Relationship to Investigational Product

The relationship of an AE to the investigational product should be determined by the investigator according to the following definitions:

 NOT RELATED: Evidence exists that the AE has an etiology other than the study drug and/or the temporal relationship of the AE/SAE to the investigational product administration makes the relationship unlikely. If an SAE is not considered to be related to study drug, then an alternative explanation should be provided. RELATED: A temporal relationship exists between the event onset and the
administration of the study drug, and makes a causal relationship possible or
probable. It cannot be readily explained by the participant's clinical state or
concomitant therapies and may appear, with some degree of certainty, to be
related based on the known therapeutic and pharmacologic actions of the drug.
Good clinical judgment should be used for determining causal assessment.

7.1.4. Unexpected Adverse Reactions

An AE is "unexpected" if its nature and severity are not consistent with the information about the study drug provided in the RSI in the voxelotor IB.

7.2. Adverse Event Reporting

7.2.1. General

All AEs will be recorded from the time the study participant signs the ICF/assent form until 28 days after the last dose of study drug (EOS) via the electronic data capture (EDC) system. The investigator is responsible for evaluating all AEs, obtaining supporting documents, and ensuring that documentation of the event is complete. Details of each reported AE must include at a minimum severity, relationship to study treatment, duration, and outcome. All (both serious and nonserious) AEs must be followed until they are resolved or stabilized, or until reasonable attempts to determine resolution of the event are exhausted.

Any participant who experiences an AE may be discontinued from study treatment at any time at the discretion of the investigator. The sponsor and the contract research organization (CRO) medical monitors must be notified of the study participant discontinuation.

7.2.2. Diagnosis Versus Signs and Symptoms

If known, a diagnosis should be recorded on the eCRF rather than individual signs and symptoms (eg, record only liver failure or hepatitis rather than jaundice, asterixis, and elevated transaminases). However, if a constellation of signs and/or symptoms cannot be medically characterized as a single diagnosis or syndrome at the time of reporting, each individual event should be recorded separately on the eCRF. If a diagnosis is subsequently established, it should be reported as follow-up information.

7.2.3. Abnormal Laboratory Values

Only clinically significant laboratory abnormalities will be recorded on the AE eCRF (eg, abnormalities that have clinical sequelae, require study drug dose modification, discontinuation of study treatment, more frequent follow-up assessments, or further diagnostic investigation). If the clinically significant laboratory abnormality is a sign of a disease or syndrome (eg, alkaline phosphatase and bilirubin 5× the upper limit of normal associated with cholecystitis), only the diagnosis (eg, cholecystitis) needs to be recorded on the eCRF.

If the clinically significant laboratory abnormality is not a sign of a disease or syndrome, the abnormality itself should be recorded on the eCRF. If the laboratory abnormality can be characterized by a precise clinical term, the clinical term should be recorded. For example, an elevated serum potassium level of 7.0 mEq/L should be recorded as "hyperkalemia".

Observations of the same clinically significant laboratory abnormality from visit to visit should not be repeatedly recorded on the AE eCRF, unless their severity, seriousness, or etiology changes.

Note: Potential drug-induced liver injury (DILI; Hy's law) cases are to be reported as SAEs (Section 7.3). For suggested actions and follow-up assessments in the event of potential DILI, refer to Appendix C. (*This note is included to support Study transition to Pfizer Pharmacovigilance processes and systems*.)

7.2.4. Worsening of Sickle Cell Disease

SCD-related AEs that are common complications associated with the study participant's SCD may not be considered to be related to voxelotor unless judged by the investigator to have worsened in severity and/or frequency or changed in nature during the study. Sickle cell disease-related AEs include, but are not limited to, the following: sickle cell anemia with crisis, ACS, pneumonia, priapism, splenic or hepatic sequestrations, stroke, leg ulcers, and osteonecrosis (Kato, 2018). These events will be recorded on the AE eCRF.

Vaso-Occlusive Crisis

Vaso-occlusive crisis (VOC) is defined as a composite of acute painful crisis and/or ACS. To allow for an assessment of VOC events, while minimizing variability in reporting and assessment, additional data will be collected for SCD-related AEs (eg, acute painful crisis, ACS events).

7.3. Serious Adverse Events, Serious Adverse Drug Reactions, and Requirements for Immediate Reporting

All SAEs, regardless of causal attribution, must be reported by the investigator or designee or site personnel within 24 hours of SAE awareness on the AE eCRF via the EDC system. If the EDC system is not available, paper SAE report forms will be used to report the SAE and faxed or emailed to the sponsor or designee. The information reported on the paper SAE report form should be entered in the EDC when it is available again.

The sponsor or designee may request additional source documentation pertaining to the SAE from the investigational site. Follow-up reports must be submitted within 24 hours of awareness, and participant identifier information (eg, name, medical record number) must be redacted in the hospital discharge summaries, autopsy reports, and/or death certificates.

Follow-up SAE information must be submitted within 24 hours of awareness as additional information becomes available.

Note: The following guidelines are included to support Study transition to Pfizer Pharmacovigilance processes and systems.

Follow-up by the investigator continues throughout the active collection period and until the AE or SAE or its sequelae resolve or stabilize at a level acceptable to the investigator. For participants who are screen failures, the active collection period ends when screen failure status is determined.

If the participant withdraws from the study and also withdraws consent for the collection of future information, the active collection period ends when consent is withdrawn.

If a participant permanently discontinues or temporarily discontinues voxelotor because of an AE or SAE, the AE or SAE must be recorded on the CRF. Investigators are not obligated to actively seek information on AEs or SAEs after the participant has concluded study participation. However, if the investigator learns of any SAE, including a death, at any time after a participant has completed the study, and they consider the event to be reasonably related to voxelotor, the investigator must promptly report the SAE to the Sponsor.

7.3.1. Reporting Suspected Unexpected Serious Adverse Reactions and Urgent Safety Issues

The sponsor or designee is responsible for reporting suspected unexpected serious adverse reactions (SUSARs) to regulatory agencies, competent authorities, IRBs/ECs, and investigators as per local laws and regulations. Fatal and life-threatening SUSARs will be submitted no later than 7 calendar days of the sponsor's or designee's first knowledge of the event and follow-up information submitted within an additional 8 calendar days, or as otherwise required per local laws and regulations. All other SUSARs will be submitted within 15 calendar days of the sponsor's or designee's first knowledge of the event. The investigator is responsible for notifying the local IRBs or ECs of all SAEs that occur at his or her site as required by local regulations or IRB/EC policies, if this responsibility resides with the site.

Investigators are required to report any urgent safety matters to the sponsor or designee within 24 hours of awareness. The sponsor or designee will inform regulatory authorities, IRBs/ECs, and investigators, as applicable, of any events (eg, change to the safety profile of voxelotor, major safety findings that may place study participants at risk) that may occur during the clinical trial that do not fall within the definition of a SUSAR but may adversely affect the safety of study participants.

